### 8.2. Primary outcome.

For the primary outcome of mean glucose (mg/dL), we will first perform a Wilcoxon signed-rank test to compare paired mean glucose values between Phase A and Phase B, and then fit a linear mixed-effects model (LME) to estimate within-person change from Phase A to Phase B while accounting for repeated measures:  $Y_{ij} = \beta_0 + \beta_1(\text{Baseline}_i) + \beta_2(\text{Phase}_j) + \eta_i + \varepsilon_{ij}$  where  $\eta_i$  is a participant-level random intercept and Phase is categorical (A vs B). If assumptions are not met (e.g., skewed residuals), we will fit a linear quantile mixed model (LQMM) as a robust alternative. Candidate covariates (pre-specified) include baseline age, sex, and BMI. Note that additional exploratory analyses may be conducted to examine other demographic variables and baseline characteristics as covariates by assessing their potential associations with CGM outcomes. Variance inflation factors will be examined to rule out multicollinearity. Results will be reported as model-based estimates, corresponding 95% confidence limits, and p-value of the corresponding hypothesis test. All analyses will be performed in R ( $\geq 4.5.1$ ).

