## 2. Study Design

Study employs a within-subject design without CGM masking, enabling the measurement of glycemic variability, where participants receive feedback every 5 minutes while wearing the CGM device. This is an observational study where participant glycemic data is observed when CGM feedback is available on their smartphone app. This design captures continuous baseline values on the primary study outcome across 20 consecutive days while recorded video-based narratives are provided by participants each day as well as during the structured interview.

Glycemic variability. The primary outcome measure for the project is glycemic variability, which will be assessed using CGM automated data capture and the Dexcom Clarity cloud. We will utilize the Dexcom G6 Pro system (<https://provider.dexcom.com/products/dexcom-g6-pro/training-resources>) to capture glycemic variability over 14-20 complete wear days, with data recorded automatically every five minutes and timestamped. Participants will change the transmitter once on day 10, as the sensor has a wear time of 10 days. Data will be transferred to the Clarity cloud using an external Dexcom reader. Subsequently, the Clarity file will be exported and sent to the statistician for processing in RC software, where all variables for the complete ambulatory glucose profile (AGP) panel for glycemic variability will be calculated. Our main outcome analyses will focus on key variables related to glycemic control. Additionally, CGM data will allow us to generate important covariates, such as the % time worn by each participant per week and the number of times a participant changed the CGM sensor.

The study consists of four sequential timepoints. At baseline, participants complete an initial assessment prior to device use. Participants then wear a CGM sensor for a 10-day period (Phase A). At the end of the first wear period, the sensor is replaced per manufacturer instructions, followed by an additional 10-day CGM wear period (Phase B). Upon completion of the second wear period, participants complete a post-study assessment visit.

Figure 1 Flowchart of screening and inclusion process

\*NDSR was collected for P50 center-level analyses.

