### **4. Demographics and Baseline Assessments**

The following are specific demographic / baseline assessments of interest for analyses.

- 1) Age
- 2) Sex
- 3) Ethnicity (NIH/OMB)
- 4) Race (NIH/OMB)
- 6) Highest level of education
- 7) Current employment status
- 8) Total household income
- 9) Health insurance
- 10) CDC prediabetes risk score
- 11) Body Mass Index (BMI)
- 12) Physical Activity Level (International Physical Activity Questionnaire [IPAQ])
- 13) Finger prick HbA1c (%)
- 14) Self-reported history of prediabetes

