### **6. Outcomes**

#### **6.1. Primary outcome**

Change in mean glucose (mg/dL) from baseline. Mean glucose will be derived from CGM data obtained from the Dexcom Clarity system. Raw glucose values will be processed and analyzed using the R statistical software package *iglu* to generate the full CGM variability metrics panel. For each participant, mean glucose will be calculated as the average of all valid CGM glucose readings within each 10-day assessment period. The outcome measure represents the change in mean glucose between the baseline 10-day assessment period and the subsequent 10-day period.

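### The primary mixed model in SAP 8.2 contains an undefined term, Baseline_i. If it is the Phase A mean, the standard error of the phase effect is too small.

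*SAP*

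**What the plan says.** SAP 8.2 compares Phase A and Phase B mean glucose with a Wilcoxon signed-rank test, and then will "fit a linear mixed-effects model (LME) to estimate within-person change from Phase A to Phase B while accounting for repeated measures". Apart from the intercept, the fixed part of the model is "\beta_1(\text{Baseline}_i) + \beta_2(\text{Phase}_j"). The text after the equation explains the random intercept and Phase (A or B). It does not explain Baseline_i.

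The same section continues: "Candidate covariates (pre-specified) include baseline age, sex, and BMI". On reporting it says: "Results will be reported as model-based estimates, corresponding 95% confidence limits, and p-value of the corresponding hypothesis test".

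Elsewhere the SAP uses the word baseline for different things:

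- Section 2, a visit before any sensor is worn: "At baseline, participants complete an initial assessment prior to device use".
- Section 2, the whole wear period: "This design captures continuous baseline values on the primary study outcome across 20 consecutive days".
- Section 6.1, the first CGM period, in defining the primary outcome: "change in mean glucose between the baseline 10-day assessment period and the subsequent 10-day period".
- Section 4, headed "Demographics and Baseline Assessments", participant characteristics, including HbA1c, BMI and the CDC risk score.

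Section 7 admits a participant to the primary analysis only with valid CGM data in both periods, so each analysed participant contributes one complete pair.

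**The concern.** Two statisticians could follow section 8.2 faithfully and fit different primary models. There are two plausible readings.

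**Reading 1: the baseline value of the outcome.** No CGM glucose exists before Phase A, and section 6.1 labels Phase A the baseline period, so Baseline_i would be the Phase A mean. That number is already the participant's Phase A response. Conditioning on it removes the positive within-person correlation that the random intercept is there to capture.

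**Reading 2: pre-device characteristics**, such as age, sex and BMI, or HbA1c. The model is then sound, and the only fault is that the term is not named.

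At stake are the confidence limits and p-value that section 8.2 will report. Section 2.1 also wants variance components for planning the next study. The SAP does not say they will come from this model, but if they did, they would be unusable on reading 1. The multicollinearity check in section 8.2 would not expose the problem: with complete pairs, a covariate that is constant within a participant is orthogonal to Phase.

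**Working it through.** **Inputs from the SAP.** n = 20 (section 2.1); two rows per participant (6.1); complete pairs (7); 95% limits (8.2). There is no planned figure to reproduce, because n = 20 was not derived from a power formula.

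**Assumptions.** The documents give neither the A–B correlation ρ nor the ratio of the phase SDs, so both are varied. REML estimation and a t reference on n−1 df are also assumed; the SAP states neither.

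**Closed form, reading 1.** Let RSS be the residual sum of squares from regressing Phase B on Phase A, and SSD the sum of squares of the paired differences about their mean. Regressing the difference B−A on A leaves the same residuals as regressing B on A, so SSD ≥ RSS always. For balanced pairs:

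- between-person mean square: MSB = RSS / (2(n−2))
- within-person mean square: MSW = SSD / (2(n−1))
- paired standard error: √(2·MSW/n)

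If MSB > MSW, the intercept variance is (MSB − MSW)/2 and the standard error is the paired one. Since MSB/MSW ≤ (n−1)/(n−2), the intercept variance cannot exceed MSW/(2(n−2)). At n = 20 that is 1/36 = 2.8% of the residual variance, however much participants truly differ.

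Otherwise the intercept variance is exactly zero, the residual variance is (RSS + SSD)/(2(2n−3)), and the standard error is at or below the paired one.

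**Approximate size.** With equal SDs, the expected MSB/MSW is about (1+ρ)/2. In a zero-variance fit the standard error is then about √((3+ρ)/4) of the paired one: √(3.5/4) = 0.935 at ρ = 0.5 and √(3.9/4) = 0.987 at ρ = 0.9.

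**Simulation, reading 1.** 100,000 datasets per setting with no true change, n = 20, equal SDs:

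| ρ | Mean SE shortfall | Type I error, 19 df | Intercept variance exactly zero |
|---|---|---|---|
| 0.3 | 8.5% | 7.0% | 97% |
| 0.5 | 6.0% | 6.3% | 92% |
| 0.7 | 3.7% | 5.8% | 79% |
| 0.8 | 2.6% | 5.5% | 68% |
| 0.9 | 1.6% | 5.4% | 53% |

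The paired t test on the same data gives 4.9% to 5.1%. Other settings, over the same range of ρ:

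- Phase B SD 0.8 of Phase A: shortfall 8.7% to 12.3%, type I error 6.9% to 8.2%.
- Phase B SD 1.25 times Phase A: shortfall 0.7% to 5.1%, type I error 5.0% to 6.1%.
- n = 15, equal SDs, 14 df: shortfall 8.2% down to 1.8%, type I error 6.8% down to 5.4%.
- n = 20, equal SDs, with 37 df in the zero-variance fits: type I error 7.7% down to 5.7%.

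**One dataset fitted directly** (n = 20, ρ = 0.8). Adding the Phase A mean left the phase estimate at −2.851 mg/dL. The standard error fell from 1.606, which is the paired value, to 1.533, and the intercept variance fell from 117.9 to about 0.

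**Reading 2.** With age, sex and BMI assumed to explain 0%, 20% or 50% of between-person variance, the shortfall is at most 1.3% and type I error is 4.9% to 5.3%.

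**Baseline_i removed.** At n = 20 the shortfall is at most 0.45% and type I error is 4.9% to 5.2%. The small remainder comes from fits at low ρ where the intercept variance is estimated as zero.

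**The case against.** The strongest reply is that the SAP never says Baseline_i is the Phase A mean. Section 2 places baseline before device use, and section 8.2 calls the CGM periods Phase A and Phase B and attaches the word baseline only to participant characteristics. On that view the only established fault is an unlabelled symbol, and most of the figures above depend on a guess. That is fair as far as it goes, and those figures are conditional on reading 1. But section 6.1, which defines the primary outcome, does call Phase A the baseline period, and section 8.2 lists age, sex and BMI separately from Baseline_i. Reading 1 therefore cannot be set aside.

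It can also be said that the uses of baseline overlap. The pre-device visit and the participant characteristics are close to one sense, and the 20-day sentence is an unlikely meaning for a single covariate. This is true, but the pre-device and Phase A senses still conflict.

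Third, the harm is small. Section 2.1 says the sample was not chosen for formal testing, the Wilcoxon test is untouched, and the larger shortfalls need a low correlation or a smaller Phase B SD, neither of which the documents support. This stands, and it is why the point is rated minor.

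Finally, the checks cover the linear mixed model with complete pairs. The quantile mixed model named as a fallback in section 8.2, and the imputation or weighting allowed in section 9, were not examined.

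**Conclusion.** The concern holds, as a minor one. Baseline_i is undefined, and that needs correcting on either reading.

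On reading 1 the reported limits and p-value are slightly anti-conservative. With equal SDs and ρ between 0.3 and 0.9, the standard error is 8.5% down to 1.6% too small, and type I error is 7.0% down to 5.4% on 19 df. The intercept variance carries no usable information about how much participants differ. On reading 2 there is no material error.

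The estimated change is not biased on either reading: with complete pairs the linear mixed model returns the mean paired difference. The Wilcoxon test and the descriptive SDs are also unaffected. The sizes rest on the assumed correlations and SD ratios, and on REML with a t reference. The ceiling of 1/(2(n−2)) on the variance ratio and the direction of the standard-error error need only REML and complete pairs.

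**What to change.** Make the primary model Y_ij = β0 + β2·Phase_j + η_i + ε_ij. With complete pairs and a positive intercept variance it equals the paired analysis on n−1 df.

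If pre-device covariates were intended, replace Baseline_i with their names, for example age, sex and BMI. With complete pairs they do not change the phase estimate.

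In either case, state that the Phase A mean is not entered as a covariate while Phase A is an outcome row. If adjustment for Phase A is wanted, use one row per participant, with Phase B or the change as the response. Use the same definition of terms in the quantile mixed model.

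The cost is about one line of SAP text and no new data. If reading 1 was intended, the interval becomes on average about 2% (ρ = 0.9) to just under 10% (ρ = 0.3) wider with equal SDs, with correspondingly less power. If reading 2 was intended, results do not materially change.

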### 8.3. Other pre-specified outcome

Descriptive statistics will be used to summarize the total minutes of videos captured and processed. For each participant, the total duration of videos will be calculated, and the following summary measures will be reported: number of participants with video data and mean  $\pm$  SD or median [IQR] total minutes of videos captured and processed.

## 9. Missing Data

Missingness will be characterized (MCAR/MAR) and addressed using likelihood-based methods and, if needed, multiple imputation or inverse probability weighting; sensitivity analyses will compare approaches.

